## **15.10 Exploratory Efficacy Endpoint: Oxygenation Index**

The Oxygenation Index is considered an exploratory variable because it is inconsistently measured across sites. Ideally, it is measured at every 24 hours and 28 days post intubation with additional endpoint determinations through cessation of mechanical ventilation. Time to normalization (last SaO2 value >95%) will be evaluated; this endpoint will also be analyzed in the same manner as the primary efficacy endpoint for the time to the successful event with the requirement to not relapse within 7 days.

The mITT population will be used for the analysis.

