## 1. SYNOPSIS

Name of Investigational Product:	RLF-100
Name of Active Ingredient:	Aviptadil
Reference Product(s):	Vasoactive Intestinal Polypeptide (synthetic)
Title of Study:	RLF-100 for the Treatment of Critical COVID-19 with Respiratory Failure
Phase of Development:	Phase 2b/3
Study Site(s):	Multi Center: University of Miami, UC Irvine, Houston Methodist, and others
Total Participant Number:	198 evaluable (mITT) subjects with Critical COVID-19 on mechanical ventilation (for <8 days), non-invasive ventilation or high flow rate nasal cannula at minimum 20L flow and 50% FIO 2
Study Duration:	60-day total follow-up
Background and Rationale:	The research to be conducted under this protocol references Phase 1 research conducted under IND 52,088 in which Vasoactive Intestinal Polypeptide (VIP) has previously shown suggestions of efficacy in the treatment of ARDS related to sepsis, pulmonary arterial hypertension and other respiratory disorders.
Objectives:	To demonstrate the efficacy of RLF-100 in improving survival and reducing respiratory distress / requirement for mechanical ventilation in patients with Critical (NIH/FDA definition) COVID-19 receiving maximum standard of care other than extracorporeal membrane oxygenation (ECMO).
Endpoint(s):	
Primary Outcome Measure:
 
 
1) Cumulative distribution of the time to respiratory failure resolution with concurrent survival through Day 28.
 
 
Key Secondary Measure:
 
 
2) NIAID Ordinal Scale for Clinical Improvement (Scores 6-8) through Day 28
 
 
Secondary Outcome Measures (through Day 28 unless otherwise specified):
 
 
3) Survival lifetable through Day 28 and through Day 60
 
4) Time to ICU discharge
 
5) Time on invasive mechanical ventilation
 
6) Time on non-invasive ventilation
 
7) Time to discharge alive
 
8) Multi-organ failure free days
 
9) NIAID Area under the curve (AUC)
 
 
Other Outcome Measures (through Day 28):
 
 
10) Respiratory Distress while on mechanical ventilation: Blood PaO2/FiO2 ratio [Time Frame: enrollment through extubation]
 
11) Oxygenation Index
 
12) Improvement in chest x-ray
 
13) IL-6, TNF<math>\alpha</math> and other inflammatory markers
 

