### ***Oxygenation Index***

The Oxygenation index is defined as:

$$OI = \frac{FiO_2 \times M_{PAW}}{PaO_2}$$

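### The exploratory 'time to normalization' event under the Oxygenation Index heading is defined by SaO2 above 95%, which is not a term in the index, so its result would not describe normalization of the index

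*Combined protocol and SAP*

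**What the plan says.** Under its Oxygenation Index heading, section 13.7 states "The Oxygenation index is defined as" FiO2 multiplied by mean airway pressure and divided by PaO2. It gives no normal range and does not say whether FiO2 enters as a fraction or a percent.

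Section 15.10 calls the index exploratory because sites measure it inconsistently. It ties measurement to ventilation: "Ideally, it is measured at every 24 hours and 28 days post intubation with additional endpoint determinations through cessation of mechanical ventilation". The event it then sets begins "Time to normalization (last SaO", and the criterion in the rest of that parenthesis is a saturation above 95%. The method for this event is "analyzed in the same manner as the primary efficacy endpoint for the time to the successful event with the requirement to not relapse within 7", the unit being days. On the analysis set it says "The mITT population will be used for the analysis".

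Four other places bear on the point:

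- The Synopsis lists the Oxygenation Index among the other outcome measures through Day 28. Its statistical methods send other ordinal and continuous outcomes to mixed model repeated measures (MMRM).
- Section 15.1 does not include the index in the hierarchical testing order.
- Section 15.9 analyses PaO2/FiO2 by MMRM, with data collection stopping when invasive ventilation ends.
- Section 16.5 lists both the PaO2/FiO2 ratio and mean airway pressure among the data to be collected.

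**The concern.** The index relates the oxygenation achieved to the support needed to achieve it. Saturation reports only the first half of that relation. Staff can hold saturation up by raising FiO2 and airway pressure, and both of those raise the index. A patient can therefore satisfy the section 15.10 event while the index is high. Equally, a patient whose support is weaned at unchanged saturation can have a large fall in the index that the event does not register.

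What is at stake is interpretation. A hazard ratio reported as time to Oxygenation Index normalization would invite the reader to conclude that lungs recovered faster, when the quantity analysed is how soon saturation rose above 95% and stayed there. The wording states a rule, so a programmer who follows it faithfully will produce the mislabelled result.

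**Working it through.** The plan gives no figure for this endpoint (no threshold, expected rate or power), so there is nothing to reproduce. The check is whether the event rule uses the quantity that the heading names.

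**Step 1: definition against event.**

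| Item | Section 13.7 (index) | Section 15.10 (event) |
|---|---|---|
| PaO2 | yes, denominator | no |
| FiO2 | yes, numerator | no |
| Mean airway pressure | yes, numerator | no |
| SaO2 | no | yes, above 95% |
| Cut-off on the index | none | none |

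The two share no term.

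**Step 2: how far the index can move while the event status stays the same.** Formula: OI = FiO2 × Paw / PaO2, with Paw the mean airway pressure. All inputs below are assumptions for illustration. PaO2 is held fixed within each row, so that saturation is the same, other things equal. The documents do not give the link between PaO2 and saturation, so the example does not claim that any row lies above 95%.

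| Assumed PaO2 (mmHg) | FiO2 0.4, Paw 10 | FiO2 0.6, Paw 15 | FiO2 1.0, Paw 20 | Highest / lowest |
|---|---|---|---|---|
| 80 | 4/80 = 0.05 | 9/80 = 0.1125 | 20/80 = 0.25 | 5 |
| 90 | 4/90 = 0.0444 | 9/90 = 0.10 | 20/90 = 0.2222 | 5 |
| 100 | 4/100 = 0.04 | 9/100 = 0.09 | 20/100 = 0.20 | 5 |

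The ratio is (1.0 × 20)/(0.4 × 10) = 5 whatever the PaO2, because PaO2 cancels. Other assumed settings would give another ratio, but the structure is the same: at fixed PaO2 the index moves in proportion to FiO2 × Paw, and the event ignores that product. With FiO2 as a percent, every entry is multiplied by 100 (the first row becomes 5.0, 11.25 and 25.0), so any cut-off on the index must state its units.

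**Step 3: what the borrowed primary-endpoint method adds.** Section 15.10 takes over the primary analysis and the 7-day no-relapse rule. Sections 13.3 and 15.3 then make death or ECMO by Day 28 a failure. These rules make the event sustained and tie it to survival. They do not bring FiO2 or airway pressure into it. The primary event itself requires freedom from ventilation and high-flow oxygen (section 13.7), but section 15.10 states no such condition for the saturation event.

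**Step 4: whether the index could be analysed.** Dividing mean airway pressure by the PaO2/FiO2 ratio gives Paw × FiO2 / PaO2, which is the index. Both are in the section 16.5 list, so the index can be computed wherever both are recorded at the same time.

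**Step 5: dating the event.** The rule refers to the last saturation value. A time-to-event analysis needs a stated reading that starts the clock on the sustained period, and section 15.10 does not say which reading that is.

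**The case against.** The strongest reply is that the defect sits in one derived analysis and that the index may be analysed elsewhere. The Synopsis lists the index itself as an outcome, its general MMRM rule could cover it as a continuous variable, and section 15.10 says the time-to-event endpoint will *also* be analysed, which may point to a companion analysis. This stands as a limit. A reader might infer that the plan contains no analysis of the index at all, and the documents do not support going that far. The general rule does not name the index, however, and section 15.10 sets out no such model. Neither repairs the label on the saturation event.

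A second reply is that one good reading on heavy support does not count as success. That is correct. The 7-day rule and the failure rule for death and ECMO already apply. Sustained saturation on high support nevertheless remains compatible with the event as written.

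A third concerns the population. A reader might infer that using mITT is itself an error, because the trial also enrols patients on "non-invasive ventilation or high flow rate nasal cannula at minimum 20L flow and 50% FIO"2, and those on high-flow cannula have no ventilator pressure. For a saturation event mITT is workable, since saturation can be measured without intubation. Some patients on non-invasive ventilation may also have a pressure recorded. The population matters only when the index itself is analysed, so it is secondary here.

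Finally, simply replacing the saturation rule with an index cut-off would create a new difficulty. A patient extubated within 7 days of meeting the cut-off has no later mean airway pressure with which to check relapse. That objection is sound and shapes the fix.

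**Conclusion.** The point holds in a narrow form. The time-to-normalization event in section 15.10 is a saturation event under an Oxygenation Index label, and its hazard ratio would not describe normalization of the index. This follows from the two definitions alone and does not depend on the illustrative values. The five-fold range only shows that the gap can be large under assumed settings. It is not an estimate of bias in this trial, and the documents do not allow the direction of any distortion to be stated.

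The severity is low. The endpoint is declared exploratory and is absent from the section 15.1 hierarchy. A reader might infer that the trial's efficacy claim is weakened. It is not: the primary conclusion, the key secondary endpoint and Type I error do not depend on this analysis.

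**What to change.** In section 15.10, before unblinding:

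1. Rename the event *time to sustained SaO2 >95%*, state which reading dates it, and do not report it as Oxygenation Index normalization. The mITT set, the 7-day rule and the failure rule for death and ECMO can stay as they are.
2. Add a separate analysis of the index itself (FiO2 × mean airway pressure / PaO2, with FiO2 units stated) as a continuous measure, by the MMRM already used for PaO2/FiO2 in section 15.9. Restrict it to observations on mechanical ventilation where the index can be computed. Present it as descriptive, because who remains ventilated is itself an outcome after randomization.
3. If an index-based time-to-event analysis is preferred to the renamed saturation event, fix the cut-off and the FiO2 units before unblinding and state how extubation within the 7-day no-relapse window counts. The documents give no index threshold, so none is suggested here.

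The cost is minor SAP wording and one added exploratory model on data that section 16.5 already lists. Sample size, the testing order and the conduct of the trial do not change.

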## **15.11 Other Exploratory Efficacy Endpoint: Improvement in Chest x-ray**

The RALES score will be ascertained by a blinded radiologist panel. The percent with improvement in chest x-ray over time will be independently determined by the panel. Percent improving will be compared

using a two-sided Fisher Exact test while the RALES score distribution over time will be displayed descriptively.

The population with available data will be used for the analysis.

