Dosage, Route of Administration, and Schedule:	Three escalating doses of RLF-100 (Aviptadil): 50, 100, and 150 pmol/kg/hour or placebo administered over 12 hours via IV infusion on successive days. If side effects cannot be managed with ICU protocol, dose reduced or halted.
Statistical Methods:	Primary endpoint (cumulative distribution of the time to respiratory failure resolution) with concurrent survival through Day 28 will be displayed by a lifetable through Day 28 and analyzed using a proportional hazard model analysis containing 4 pre-defined baseline covariates and randomized treatment group (primary) as well as an unstratified log rank test (secondary). Primary endpoint ascertainment requires that recovery from respiratory failure be maintained for at least 7 days without relapse. The cumulative distribution will be constructed through Day 28 with no censoring for death or withdrawal; such patients will be regarded as failures. Other time to event outcomes will be similarly analyzed with the exception of survival which will censor for any withdrawals. NIAID Score will be analyzed by carrying forward any early deaths through Day 28; other ordinal and continuous outcomes will be assessed by mixed model repeated measures through Day 28. The primary analysis will be based on the modified intent-to-treat (mITT) population to be based on all treated patients.

Sample Size Calculation:	For the primary efficacy endpoint, assuming a 40% success percent in the placebo group by Day 28 and a 62% success percent in the RLF-100 group by Day 28, for log rank test with two-sided overall 5% Type I error and 81% power, the sample size to detect a 22% absolute improvement in the percent achieving respiratory failure resolution by Day 28 (from 40% to 62%) is 198 subjects in the primary analysis group (2:1 randomization favoring the RLF-100 group). A 20% absolute advantage in the percent achieving respiratory failure resolution by Day 28 is deemed to be clinically meaningful.
Interim Analyses	An interim look for safety and futility will be conducted once the first 21 randomized subjects complete Day 7. A second interim look for safety, futility, and efficacy will be conducted once the next 81 subjects complete Day 28 but the study will not be prematurely stopped for efficacy.

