### ***Improvement in Chest x-ray***

Chest x-ray images will be collected (1) pre-treatment, (2) 48-96 hours post start of infusion, (3) 1 week  $\pm$ 2 days post start of infusion, and (4) two weeks  $\pm$  2 days post start of infusion, provided the patient is still hospitalized. All x-rays will be read by a blinded radiologist panel and scored according to the Rapid Assessment of Lung Edema (RALE) score (Warren 2017).

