Urine Leukotriene f,j		X		X		X			X		X		X		
Plasma: VIP (Vasoactive Intestinal Polypeptide) f,j		X		X		X			X		X		X		
Study Drug Pharmacy Dispensing		X		X		X									
Assess for Adverse Events d		X	X d	X	X d	X	X d	X	X	X	X	X	X		
Assess Concomitant Medications	X	X		X		X		X	X	X	X	X	X		
NIAID Ordinal Scale for Clinical Improvement		X		X		X		X	X	X	X	X	X	X	X
Chest X-ray (sub-study sites only) i	TBD =>														

Footnotes:

a	Each dose is administered over 12 hours at the same time each day. Date and time of start and end of infusion will be recorded.
b	Pulse and respirations will be continuously monitored but will be recorded prior to and at 2, 4, 6, 8, 10 and 12-hour timepoints after each dose escalation.
c	Blood pressure will be recorded prior to infusion and at 2, 4, 6, 8 and 12-hour timepoints throughout the infusion.
d	Infusion reactions/adverse events check at 2 hours, and then continuously throughout the 12-hour infusion period.
e	Collected pre-dose, 2 hours and 12 hours after the start of each infusion over 3 days, then on Day 5, Day 7 and Day 28 / or day of discharge if sooner.
f	Plasma VIP and urine leukotriene E4 should be collected prior to initiating each dose escalation, on days 1, 2,3; then at day 5, day 7 and day 28 or day of discharge if sooner.
g	Only on Day 10.
h	Ventilated Patients only - ABGs as follows: Days 1, 2 and 3 - Pre-Dose and at 6 hours after infusion begins ( $\pm$ 1 hour). Day 4 through discharge - once daily.
i	Chest X-ray images to be captured via a sub-study at a subset of identified sites only, specifics on X-ray timings and number TBD.
j	Procedures for blood samples for cytokines; urine leukotriene; and plasma VIP are not required after 165 evaluable patients have been enrolled.

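### Section 15.11 tests only an undefined yes/no chest x-ray improvement and leaves the numeric RALE score untested; minor, cheap to mend, with a power cost the documents cannot fix

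*Combined protocol and SAP*

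**What the plan says.** Section 13.7 (Improvement in Chest x-ray) plans one pre-treatment film and three later ones, at 48-96 hours, one week and two weeks, the later films depending on the patient still being in hospital. On reading, it states: "All x-rays will be read by a blinded radiologist panel and scored according to the Rapid Assessment of Lung Edema (RALE) score".

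Section 15.11, headed as exploratory, defines the outcome this way: "The percent with improvement in chest x-ray over time will be independently determined by the panel". Percent improving is compared "using a two-sided Fisher Exact test while the RALES score distribution over time will be displayed descriptively". On the analysis set it adds: "The population with available data will be used for the analysis".

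Three other places bear on the point:

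- Synopsis, Statistical Methods: "other ordinal and continuous outcomes will be assessed by mixed model repeated measures through Day 28".
- Section 14.4 lists chest x-ray findings among the categorical variables to be summarised by frequency.
- Appendix A, footnote i: "Chest X-ray images to be captured via a sub-study at a subset of identified sites only, specifics on X-ray timings and number TBD".

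The testing hierarchy in Section 15.1 does not include chest x-ray.

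**The concern.** The plan pays for a graded, blinded reading of each film and then bases its only formal comparison on a yes/no judgement. If that judgement follows the score, small and large improvements count alike, as do no change and marked worsening. Whether or not it follows the score, no test in 15.11 uses the size of change in RALE or the pre-treatment RALE score. The yes/no outcome is also not reproducible as written: the panel is given no threshold, and with up to three later films it is unclear which one decides.

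Chest x-ray is the only imaging measure of lung injury among the listed outcomes. A real shift in lung edema could be visible in the displayed scores and still yield an uninformative test. The plan gives no reason for preferring the yes/no outcome here, whereas it ties the NIAID 6-8 cut to the remdesivir approval (Sections 13.6 and 13.7).

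**Working it through.** **1. The sections side by side.** The Synopsis would send a numeric score to MMRM. Section 14.4 treats chest x-ray findings as categorical and descriptive. Section 15.11 tests a proportion and describes the score. Section 15.9 does the reverse for PaO2/FiO2: it models the continuous measure by MMRM and gives the percent improving by at least 100 points as a descriptive statistic. The proposed approach is thus already in the plan for a neighbouring outcome.

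**2. Inputs for a power illustration.**

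- From the documents: a two-sided Fisher exact test (15.11), 2:1 allocation (10.8), and 132/66 patients (10.7) as a ceiling if every patient had films.
- Borrowed: 40% v 62%, the primary-endpoint rates in the Synopsis, and the 5% two-sided level used elsewhere in the plan.
- Assumed: sub-study sizes of 66/33 and 40/20; improvement is a cut of a normally distributed change score; follow-up is complete.
- Not in the documents: RALE SD, treatment effect, improvement rates, and number of patients with films.

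**3. The plan's own figure.** The only power stated is 81% for the primary endpoint with 198 patients at 40% v 62%. Exact enumeration of the Fisher test at 132/66 with those rates gives 82.3%, close to it. The plan's figure is for a log-rank test, so this checks the inputs and the enumeration only. No power is stated for chest x-ray.

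**4. Fisher v t-test.** The standardised difference implied by the two rates is

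d = probit(0.62) − probit(0.40) = 0.305 + 0.253 = 0.559 (from unrounded values).

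The t-test noncentrality is d / √(1/n_active + 1/n_placebo). Fisher power sums the two binomial distributions over all tables with p ≤ 0.05.

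| Active/placebo | Noncentrality | Fisher | t-test | Difference (points) |
|---|---|---|---|---|
| 132/66 | 3.71 | 82% | 96% | 14 |
| 66/33 | 2.62 | 47% | 74% | 27 |
| 40/20 | 2.04 | 29% | 52% | 23 |

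**5. Other rates.** For placebo/active improvement of 30/50, 50/70, 60/80 and 70/85%, the difference is 16-27 points at 132/66, 23-31 at 66/33 and 18-24 at 40/20.

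**6. Wider grid.** With placebo improvement from 30% to 80% and d from 0.3 to 0.8, the loss is 1-37 points at N=198, 11-41 at N=99, 7-41 at N=60 and 4-35 at N=30. The end points depend on grid spacing: at N=99 with placebo 80% and d = 0.7, Fisher gives 47.8% and the t-test 90.2%, a gap of 42. The loss is smallest where both tests are near 100% or both have little power.

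**7. Baseline-adjusted score.** Two sets of simulations used an integer score bounded 0-48, with the range, SDs and baseline relation all assumed.

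- In the first, with a 4.5-point effect, Fisher v ANCOVA was 76% v 96% at 132/66 and 45% v 74% at 66/33. With heavy-tailed residuals it was 88% v 98% and 59% v 80%. ANCOVA Type I error was 4.9-5.8%.
- In the second, over d of 0.3 to 0.7, ANCOVA gained 4-31 points at N=198, 18-38 at N=99 and 11-43 at N=60.

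The score-based test had the higher power in every setting run.

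**The case against.** The strongest objection is that 15.11 does not say improvement is a cut of the RALE change. The panel determines it independently, and that may mean a separate global reading of the films. A reader might infer that the plan dichotomises the RALE score and so loses a known amount of power, say 13 to 30 points. The documents support neither step. They state no cut-off, and that range arises only with films in all 198 patients, placebo improvement of about 40-70% and a standardised effect of about 0.40-0.56. This objection stands: the figures are illustrative.

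A reader might also infer that the scores will exist for the whole trial. They will not: Appendix A limits films to a subset of sites with the number undecided, and Section 13.7 stops them at discharge. At small sizes power is low either way (29% v 52% at 40/20). The calculations assume complete follow-up, so the gain is not shown under the plan's actual pattern of missing films. That also stands, and any test of the score needs a rule for death and discharge. It is no reason to keep the Fisher test, which uses the same available films and has the same selection problem.

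Nor do the documents support a flat breach of the plan's own rule. The listed endpoint is improvement, Section 14.4 treats x-ray findings as categorical, and other sections depart from the Synopsis summary, such as the t-tests for NIAID AUC (15.7) and VIP (15.12). What stands is that the sections need reconciling.

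Finally, the endpoint is exploratory, outside the hierarchy, and its scores are displayed over time. That limits the consequence but does not explain why the graded score goes untested.

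**Conclusion.** The point holds as a minor one. Section 15.11 formally tests only a panel-determined yes/no improvement with no stated cut-off or time point, and leaves the RALE score and its pre-treatment value out of any test. The direction of the power loss is clear if improvement tracks the score; its size is not. It is 14, 27 and 23 points in the three illustrative cases, and about 1 to 41 points over the wider assumptions. If improvement is judged separately from RALE, no loss can be computed and the figures serve only as an analogy. The gap in definition and the untested graded score remain in either case. No label claim depends on this endpoint.

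**What to change.** Amend Section 15.11 before the SAP is finalised:

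- Test the RALE score with the MMRM named in the Synopsis, over the scheduled post-treatment films, or with ANCOVA at one named film. Adjust for pre-treatment RALE and the four pre-defined covariates. Use a rank-based version if residuals are clearly skewed.
- State how death and discharge before a scheduled film are handled, given that films exist only at sub-study sites and while the patient is in hospital.
- Define improvement, say whether it derives from RALE, and name the film that decides it.
- Keep percent improving, with its interval, as a descriptive summary, as Section 15.9 does for PaO2/FiO2.
- Reconcile the Synopsis, Section 14.4 and Section 15.11 on method, and Section 13.7 with Appendix A on sites and film times.

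The cost is about a paragraph of wording and one extra model, with no new films, readings or patients. The downside is that a mean score difference is less intuitive than a percent improved, which is why the percent stays as a description.

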## 13.3 Intercurrent Events

Given that this is an ICU study, the standard practice is to use the ICH E9 (R1) "treatment policy strategy" where all additional treatments given to the patient are considered to be part of care in both treatment groups. Thus, the analysis does not control for them but rather ignores them. Both remdesivir and dexamethasone will be considered in this way since there are no approved indications for Critical COVID-19. The treatment policy strategy is based on the ICH E9 ITT Principle. Thus, the occurrence of an intercurrent event is considered irrelevant in defining the treatment effect of interest; the value for the variable of interest is used regardless of whether or not the intercurrent event occurs. For example, when specifying how to address use of additional medication as an intercurrent event, the values of the variable of interest are used whether or not the patient takes additional medication. The study further benefits in that study treatment is limited to three days so any subsequent intercurrent event is considered to be part of the treatments being compared. One situation where the treatment policy strategy cannot be implemented for intercurrent events that are terminal events, e.g. going on ECMO or dying since values for the variable after the intercurrent event do not exist; then the estimand based on this strategy cannot be constructed with respect to a variable that cannot be measured due to death or being put on ECMO. Thus, dying or going on ECMO will impose a failure on all time to event outcomes other than survival.

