## 13.4 Dropouts

Dropouts are not expected given that this is an ICU study. In the event of dropouts (including early withdrawals), these events will be reviewed at a Biostatistics Data Review Meeting (BDRM) to determine (in a blinded manner) the impact on each efficacy endpoint as well as an alternative impact to be applied in sensitivity analyses. The general approach will be to consider early withdrawals from a best practices perspective; for example, a patient going home on Day 10 who refuses follow-up at Day 28 and Day 60 is likely alive where a patient being transferred to a hospice is to be assumed as dead at Day 28 and Day 60.

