## 14.4 Statistical Methods

The primary analyses will be based on the modified intent-to-treat (mITT) population.

All analyses will be conducted according to the treatment policy strategy to handle intercurrent events. In the event of any dropouts, the BDRM will discuss how to best count these patients in the primary analysis and then in a sensitivity analysis.

Evaluation of the primary efficacy endpoint (cumulative distribution through Day 28) will be analyzed by a pre-defined proportional hazard model to include age (<65,  $\geq$ 65 years), baseline NIAID score (2,  $>$ 2), RDR (<150 mmHg,  $\geq$ 150 mmHg), previous anti-viral therapy for COVID-19 (none, any), and study treatment as covariates (primary); the proportional hazard model will be used to estimate unbiased treatment effects while controlling for these four baseline covariates. To count in the accruing numerator, the event must be confirmed by the site to last for at least 7 days with Day 28 survival. SAS PROC PHREG will be used for these analyses. See Sections 13.3-4 for rules to count respiratory failure resolution and the handling of intercurrent events and dropouts.

The key secondary efficacy endpoint will be the percent achieving a NIAID Score 6-8 by Day 28/exit (primary) and by Day 60 (secondary) and will be analyzed by comparing success percents. Patients who die or withdraw will not be counted as achieving success (event). The primary analysis will be a logistic regression model containing the same covariates as the primary efficacy endpoint. The percents achieving success by Day 28/exit will also be compared using a two-sided Fisher Exact test.

The survival curve will be displayed using Kaplan-Meier lifetables to account for censoring in the estimation of the Day 28 and Day 60 survival outcomes; Greenwood's formula will be used to estimate Day 28 outcomes with two-sided 95% confidence intervals constructed to compare the treatment group differences. The same proportional hazard model as for the primary efficacy endpoint will be used to analyze survival; in addition, an unstratified log rank test will be performed.

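### Chest x-ray improvement is compared only in patients with available films, so at 1 and 2 weeks discharges and deaths can leave the denominator and bias this exploratory comparison in either direction

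*Combined protocol and SAP*

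**What the plan says.** - **When films are taken.** Section 13.7 (Improvement in Chest x-ray) lists four: pre-treatment, 48-96 hours, 1 week ± 2 days and 2 weeks ± 2 days after the start of infusion, "provided the patient is still hospitalized". Section 11.1 says that return visits and home visits after discharge are impractical.
- **What is compared.** In 15.11 a blinded radiologist panel judges improvement. Percent improving is compared "using a two-sided Fisher Exact test while the RALES score distribution over time will be displayed descriptively". No time point is named.
- **In whom.** Section 15.11 states: "The population with available data will be used for the analysis". The neighbouring sections 15.9, 15.10 and 15.12 name the mITT population.
- **Rules for missing outcomes.** Under 13.3, "dying or going on ECMO will impose a failure on all time to event outcomes other than survival". Section 13.4 sends dropouts and early withdrawals to a data review meeting "to determine (in a blinded manner) the impact on each efficacy endpoint as well as an alternative impact to be applied in sensitivity analyses".
- **Where films are taken.** Appendix A, footnote i: "Chest X-ray images to be captured via a sub-study at a subset of identified sites only, specifics on X-ray timings and number TBD". Section 13.7 mentions no restriction to certain sites.
- **Status.** The heading of 15.11 calls the endpoint exploratory, the Synopsis lists it under other outcome measures, and the testing order in 15.1 omits it.

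**The concern.** Whether a patient has a 1- or 2-week film depends on being alive and still in hospital on that day. Both are outcomes the drug is intended to change: time to discharge alive and survival are secondary endpoints. A comparison among those with films then sets apart two groups that randomization did not create.

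If the drug shortens stay, its best responders are under-represented at the later films. If it changes mortality, the severity mix of those left in hospital shifts as well. A real benefit could be understated or reversed, and an excess of deaths on drug could make the drug look better than it is. A reader of the final table could not tell which had happened.

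**Working it through.** **No plan figure to reproduce.** The documents give no expected rate, sample size or power for this endpoint. What follows illustrates the mechanism and does not estimate its size in this trial.

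**Do other rules close the gap?** Percent improved is a proportion, not a time-to-event outcome, so the failure rule in 13.3 does not reach it. Section 13.4 deals with dropouts and withdrawals and gives no rule for a film missing through discharge or death. Neither closes it.

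**Illustration 1: discharge only, Day 14.** Inputs:
- Resolution by Day 28 of 40% on placebo and 62% on drug (Synopsis; 14.5). Section 14.2 prints 50% for the drug arm and 15.3 more than 50%; 62% is used because it matches the stated 22-point difference.
- Assumed: constant hazards; all resolved patients have improved films; a share *q* = 30% of unresolved patients improved in both arms; deaths ignored.
- Assumed and varied: *f*, the share of resolved patients who have left hospital by Day 14.

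Resolved by Day 14:
- Placebo: R = 1 − 0.60^(14/28) = 22.5%
- Drug: R = 1 − 0.38^(14/28) = 38.4%

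True percent improved, R + *q*(1 − R):
- Placebo: 0.225 + 0.3 × 0.775 = 45.8%
- Drug: 0.384 + 0.3 × 0.616 = 56.8%
- Difference: 11.1 points before rounding

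Percent improved among those with a film: [(1 − *f*)R + *q*(1 − R)] / (1 − *f*R).

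| Share of resolved patients who have left (*f*) | Placebo | Drug | Difference shown |
|---|---|---|---|
| 0 | 45.8% | 56.8% | 11 points |
| 0.5 | (0.113 + 0.232)/0.887 = 38.9% | (0.192 + 0.185)/0.808 = 46.6% | about 8 points |
| 1 | 30% | 30% | 0 points |

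The 30% is also a guess. The true difference is (0.384 − 0.225)(1 − *q*): about 12.7 points at *q* = 20% and 7.9 points at *q* = 50%. At *f* = 1 the available-film comparison shows 0 whatever *q* is, provided *q* is equal in the two arms.

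**Illustration 2: deaths included, 2-week film.** All rates are assumptions. All-patient success counts live discharges as improved and deaths as not improved.
- *Sicker patients left on drug.* Placebo: 20% discharged, 20% dead, 35% improved among those remaining. Drug: 42%, 14%, 25%. All patients: 0.20 + 0.60 × 0.35 = 41.0% v 0.42 + 0.44 × 0.25 = 53.0%, or +12 points. With films: 35% v 25%, or −10 points.
- *More deaths on drug.* Placebo: 20% discharged, 15% dead, 35% improved. Drug: 20%, 30%, 45%. All patients: 0.20 + 0.65 × 0.35 = 42.8% v 0.20 + 0.50 × 0.45 = 42.5%, or about 0. With films: 35% v 45%, or +10 points for drug.

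The bias can hide a benefit, reverse it, or create one.

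**The case against.** The strongest defence has four parts.

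1. The endpoint is exploratory and supports no label claim. This stands, and it limits the importance of the point.
2. Section 15.11 names no time point and speaks of improvement over time. A patient discharged on Day 8 would normally have a 48-96 hour film and perhaps a 1-week film, and might be classified from those. This stands too: early discharges can leave the comparison, but the text does not say that they must.
3. Some restriction to available films is unavoidable, since Appendix A confines films to some sites and no one returns after discharge. That is true of collection. It does not settle the denominator, which the SAP can define.
4. Resolution of respiratory failure is not discharge. Section 13.7 defines it as being off ventilation and high-flow oxygen, and discharge alive is a separate endpoint, so many resolved patients may still be in hospital and filmed. This is why the illustration runs from 0 to 11 points.

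A reader might infer that 15.11 contradicts 14.4, which states: "All analyses will be conducted according to the treatment policy strategy to handle intercurrent events". The documents do not support that. Section 13.3 frames the strategy around additional treatments, says it cannot be applied to death or ECMO, and does not name discharge. What is left is a gap. Nor is it an error to test the panel's judgement and only describe the RALE score; that is a legitimate choice for an exploratory endpoint.

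**Conclusion.** The point holds and is minor. Following 15.11 as written, the 1- and 2-week comparisons condition on discharge and survival, and no other section repairs this. The direction of the bias is not known in advance.

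A reader might infer that a real benefit will vanish from this endpoint. The documents do not support that as a general result. The 0-point outcome in the first illustration needs every resolved patient to have gone home by Day 14 and equal improvement among the rest. With half gone, about 8 of 11 points remain. The documents give no discharge rate, no death rate by arm and no rate of film improvement, so the size cannot be fixed.

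The primary result and the hierarchical tests are unaffected. The mismatch between 13.7 and Appendix A footnote i on sites, timing and number of films is a separate inconsistency, and it stands whatever the size of the bias.

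**What to change.** Amend 15.11 as follows:
- **Denominator:** all mITT patients at sub-study sites with a pre-treatment film.
- **Main comparison:** the 48-96 hour film, since the fewest patients have left by then.
- **Later films:** count deaths and ECMO as not improved, extending the 13.3 rule to this endpoint. Classify patients discharged alive by their last film, with a sensitivity analysis that counts them as improved.
- **Reporting:** number of films, and reason for each missing film, by arm and time point.
- **RALE score:** if it is to be tested by ANCOVA on the pre-treatment score, limit this to the 48-96 hour film, because the method has no place for deaths or discharges.

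Reconcile the four film times in 13.7 with Appendix A footnote i.

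The cost is SAP wording before database lock, with no extra films or readers. The downside is that using the last film is a convention. In the first illustration with *f* = 1, if a share *g* of discharged patients had improved by their last film, the difference becomes 0.158*g* − 0.047 (0.384 − 0.225 = 0.158 before rounding; 0.3 × (0.616 − 0.775) = −0.047). That gives the full 11 points only at *g* = 1 and 0 at *g* = 0.30. Hence the sensitivity analysis and the early film as the main comparison.
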